## 10.2 LIST OF ANTICIPATED POTENTIAL ADVERSE EVENTS

Anticipated potential adverse events listed below include those that might reasonably be expected to occur in this study because they are associated with glaucoma, ab-interno transluminal viscoelastic delivery, trabeculotomy, and/or the risk analysis for OMNI System. Adverse events may occur intra-operatively or post-operatively.

- [REDACTED]

 To avoid double counting an event, events of IOP  $\geq$  10 mmHg above baseline IOP at  $\geq$ 1 month visit that require management with systemic medication or secondary surgical intervention should be reported as “IOP increase requiring management with systemic medication at  $\geq$ 1 month visit” or “Need for secondary surgery intervention to manage IOP,” respectively.

 Hypotony is defined as “early” if it occurs within 2 weeks of surgery and “late” if it occurs more than 2 weeks after surgery

---

•

### 10.3 REPORTING ADVERSE EVENTS AND UNANTICIPATED ADVERSE DEVICE EFFECTS

Identification, collection and reporting of adverse event information is the responsibility of the principal investigator. The investigator records the date of the event, its severity, treatment (if any) and the assessed relationship of the event to the study device on the Adverse Event Case Report Form (AE CRF).

Any ocular-related **serious adverse event (SAE)** should be reported to the study sponsor within one business day of learning of the event. Non-ocular-related SAEs should be reported to the study sponsor within two working days of learning of the event. Email the AE CRF to [[contact]](mailto:[contact]).

Any **unanticipated adverse device effects (UADE)** must be reported to the following two entities:

1. The study sponsor – Within one working day of the investigator first learning of the event, e-mail the AE CRF to [[contact]](mailto:[contact]); and
2. The reviewing IRB – As soon as possible, but no later than 10 working days after the investigator first learns of the event, report per the IRB's instructions.

The sponsor will conduct an evaluation of unanticipated adverse device effects. If the sponsor determines that an unanticipated adverse device effect presents an unreasonable risk to subjects, parts of the investigation presenting risks will be terminated. Termination will occur no later than 5 working days after the sponsor

makes such a determination and no later than 15 working days after the sponsor first received notice of the effect.

## 11 STATISTICAL CONSIDERATIONS

### 11.1 SAMPLE SIZE CALCULATION

The sample size calculation is based on the following statistical hypotheses and assumptions for the primary and secondary effectiveness endpoints.

#### Primary Effectiveness Endpoint

The statistical hypotheses for the primary effectiveness endpoint, proportion of eyes with a  $\geq 20\%$  reduction in unmedicated mean diurnal IOP at the 12-month postoperative examination (P1), are  $H_0: P1 \leq 0.4$  and  $H_a: P1 > 0.4$ . The performance goal of 0.4 is based on Ahmed et al. that 56% of Hydrus pseudophakic eyes had an outcome of 0 medications and 20% IOP reduction and 11% of 2-iStent eyes had the same outcome. The average of these two reported rates of 0 medications with IOP reduction of  $\leq 20\%$ , 33.5%, was used for determining the performance goal of this study. However, the article mentioned that 20% of 2-iStent eyes did not have the terminal hypotensive medications washout. As such, the rate of 11% of the 2 iStent eyes might be an under-estimation of the true rate of unmedicated IOP reduction of  $\leq 20\%$ . Therefore, a performance goal of 40% (the closest integer larger than 33.5%) is used as the performance goal of the primary effectiveness endpoint of the study.

Based on the adjusted normal distribution approach with a one-sided significance level of 0.025 (or two-sided 0.05), a sample size of **91** eyes with evaluable data at 12 months provides a statistical power of 80% at a true  $P1 = 0.55$ .

Only the study results demonstrate that the device is effective based on the primary effectiveness endpoint (i.e. one-sided p-value  $< 0.025$ ), the formal statistical and clinical conclusions for the secondary effectiveness endpoints will be performed. Therefore, the overall two-sided significance level for the secondary effectiveness endpoints will be 0.05.

[REDACTED]

[REDACTED]

---

 Iqbal [name], [name], PhD, [name], et al. A Prospective Randomized Trial Comparing Hydrus and iStent Microinvasive Glaucoma Surgery Implants for Standalone Treatment of Open-Angle Glaucoma, The COMPARE Study. *Ophthalmology*. 2020 Jan;127(1):52-61.

[REDACTED]

[REDACTED]

[REDACTED]

[REDACTED]

[REDACTED]

[REDACTED]

[REDACTED]

[REDACTED]

[REDACTED]

[REDACTED]

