### **11.4.1 PRIMARY EFFECTIVENESS ENDPOINT**

Proportion of eyes with a  $\geq 20\%$  decrease in unmedicated mean diurnal IOP at the 12-month postoperative examination compared to baseline will be calculated. The binomial distribution will be used to derive the exact 95% confidence interval of the percent. The

proportion will be compared against the performance goal of 0.4 (or 40%) based on binomial distribution.

[REDACTED]

For the analyses based on the ITT population, the following imputation for subjects with missing 12-month data but without SSI may be performed:

- The within-eye worst IOP (collected after 3 months postoperatively or IOP at baseline for the subjects with no data after postoperative 3 months) for the missing 12-month IOP and worst number of IOP lowering medications (collected after 3 months postoperatively or IOP-lowering medication data at baseline for the subjects with no data after postoperative 3 months) for the missing 12-month number of IOP-lowering medications.
- The worst IOP (collected after 3 months postoperatively or IOP at baseline for the subjects with no data after postoperative 3 months) during the study for the missing 12-month IOP and worst number of IOP-lowering medications (collected after 3 months postoperatively or IOP-lowering medication data at baseline for the subjects with no data after postoperative 3 months) during the study for the missing 12-month number of IOP-lowering medications.
- The mean IOP during the study for the missing 12-month IOP and mean number of IOP-lowering medications during the study for the missing 12-month number of IOP-lowering medications.
- The last-observed-carried-forward approach.

**11.4.2** [REDACTED]

[REDACTED]

[REDACTED]

[REDACTED]

- [REDACTED]

[REDACTED]

[REDACTED]

[REDACTED]

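### Is the 40% performance goal undermined because the next integer above 33.5% is 34%?

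*Combined protocol and SAP*

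**What the plan says.** Section 11.1 (Primary Effectiveness Endpoint) tests whether the 12-month responder rate exceeds 0.4. It takes two rates from a cited randomized comparison of two microstents: "56% of Hydrus pseudophakic eyes had an outcome of 0 medications and 20% IOP reduction and 11% of 2-iStent eyes had the same outcome". Their average, "33.5%, was used for determining the performance goal of this study".

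The section then gives a reason for going higher. It says that "the article mentioned that 20% of 2-iStent eyes did not have the terminal hypotensive medications washout" and that "the rate of 11% of the 2 iStent eyes might be an under-estimation of the true rate of unmedicated IOP reduction of" the stated size. It concludes that "a performance goal of 40% (the closest integer larger than 33.5%) is used as the performance goal of the primary effectiveness endpoint". No corrected 2-iStent rate and no corrected average are given.

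The benchmark outcome is printed twice with the sign ≤20%, once in the sentence beginning "The average of these two reported rates of 0 medications with IOP reduction of" and once in the under-estimation sentence. The trial's own endpoint is a reduction of ≥20%.

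Section 11.4.1 carries the same value forward: the "proportion will be compared against the performance goal of 0.4 (or 40%) based on binomial distribution". An exact 95% confidence interval is planned there as well.

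**The concern.** In a single-arm study the performance goal is the only comparator, and this paragraph is the only support for it that can be read. The stated rule gives 34%, not 40%. The washout remark gives a direction but no amount. For the average to be 40%, the 2-iStent rate would have to be 24%, which appears nowhere. Read literally, the ≤20% sign would also turn the benchmark into a rate of non-response.

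The value matters because formal conclusions on the secondary endpoints depend on it; they follow only if the primary test succeeds ("Only the study results demonstrate that the device is effective based on the primary effectiveness endpoint"). If 0.4 were a miscalculation, the trial might be testing the wrong null. If it stood for an unstated corrected benchmark, a narrow pass might be read as beating the published devices without having shown it.

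**Working it through.** **Inputs (Section 11.1).** Published rates 56% and 11%; 20% of 2-iStent eyes without terminal washout; null 0.40; assumed true rate 0.55; one-sided level 0.025; 91 evaluable eyes; adjusted normal method. Section 11.4.1 supplies the binomial test against 0.4.

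**1. The plan's own sample size.** Without continuity correction:

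n = [1.960·√(0.40·0.60) + 0.842·√(0.55·0.45)]² / 0.15² = 84.5

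With continuity correction:

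n/4·[1 + √(1 + 2/(84.5·0.15))]² = 91.05

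Continuity-corrected power at 91 eyes is 79.98%. So 91 was computed with 0.40 as the null. The same formula with a null of 0.34 gives 45.8, or 46 eyes. The goal of 40% is what the design was built on, not a misprint of 34%.

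**2. The average.** (56 + 11)/2 = 33.5. The next integer is 34 and the next multiple of ten is 40. The parenthetical is false as written, and true if integer is replaced by multiple of ten.

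**3. Effect on the pass rule (exact binomial, 91 eyes, one-sided 0.025).**

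| Null | Responders needed | Exact size | Power at 0.55 |
|---|---|---|---|
| 0.34 | 41 (45.1%) | 0.0186 | 97.8% |
| 0.40 | 47 (51.6%) | 0.0161 | 77.3% |

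The goal in use asks for six more responders than the literal rule would.

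**4. What the washout remark could be worth.** The plan does not give the denominator of the 11%, so both readings are assumptions. The 56% is left as printed. Let f be the share of unwashed 2-iStent eyes that would have been responders.

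- *The 11% is of all 2-iStent eyes, with unwashed eyes counted as failures.* The rate is 11 + 20f. The average is 33.5% at f = 0. It is 34.9% if unwashed eyes respond like washed ones (11/0.8 = 13.75%), and 43.5% at the extreme f = 1. An average of 40% needs f = (24 − 11)/20 = 65%.
- *The 11% is of washed eyes only.* The rate is 0.8·11 + 20f = 8.8 + 20f. The average is 32.4% at f = 0, 33.5% at equal response and 42.4% at f = 1. An average of 40% needs f = (24 − 8.8)/20 = 76%.

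So 40% lies inside the possible range on either reading. It is well above the equal-response value on both.

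**5. What the narrowest pass shows.** For 47 of 91 the exact lower limit is 40.93%. It exceeds the corrected average whenever f is below:

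- first reading: (2·40.93 − 56 − 11)/20 = 74%
- second reading: (2·40.93 − 56 − 8.8)/20 = 85%

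At equal response the benchmark is 34.9% or 33.5%, and every passing result excludes it.

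**The case for a change.** The strongest contrary case is that a plainly false statement about the null value should not stand in a single-arm plan. The multiple-of-ten reading is an inference. It would also mean that the washout argument did no numerical work, although the text presents 40% as its consequence. Prior results with this device cannot fill the gap, because Section 5 says they will not be used for the study's assumptions. And a pass at 47, 48 or 49 responders (lower limits 40.9%, 42.0%, 43.1%) does not clear the extreme 43.5%; only 50 (44.2%) does.

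Some of this stands. The parenthetical is wrong, the basis for 40% is not spelled out, and the ≤ signs do not fit the endpoint. The argument about narrow passes is weak, because it needs unwashed eyes to respond at about 74% or more where washed eyes respond at 13.75% (or 85% against 11%). The plan as it can be read also claims nothing about superiority to a washout-corrected benchmark; it tests against 0.4 and reports an exact interval, which any reader can set beside 33.5% or another figure. The ≤ sign misleads no one in practice, since the same paragraph introduces the outcome as zero medications with a 20% reduction and defines the endpoint as ≥20%.

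The exact power of 77.3%, against the stated 80%, comes from sizing by a normal approximation and testing exactly. It is a separate matter from how 40% was explained.

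**Conclusion.** The concern is right about the wording and has no consequence for the trial. The integer above 33.5 is 34, and the step to 40 is a clerical slip or an unstated rounding up in the direction the text itself argues for. The null of 0.4 appears consistently in Sections 11.1 and 11.4.1, reproduces 91 eyes, and is 6.5 percentage points above the published average. Following the plan as written gives a valid test of whether the responder rate exceeds 40%. Rewording the justification would leave the null, sample size, pass mark of 47 and reported interval exactly as they are.

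The pass marks, power and sample size rest only on figures in the plan. The statements about the corrected benchmark rest on an assumed denominator for the 11% and on taking the 56% as printed, so they are illustrative.

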## **11.2 ANALYSIS POPULATIONS**

The intent-to-treat (ITT) analysis population includes all subjects who are enrolled and treated, regardless of whether or not they have a protocol deviation. The per-protocol analysis population (PP) is a subset of ITT, which includes all subjects who have ab-interno transluminal viscoelastic delivery and trabeculotomy, 12 month IOP (or hypotensive medications washed out IOP if the medications can be washed out) and medication data, and have no clinically significant protocol deviations. It should be noted that the ITT subjects with an uneventful study procedure but with SSIs before the 12-month visit will be included in the PP population even if they do not have the 12-month IOP and medication data. The primary analyses on the primary and secondary endpoint analyses will be carried out on the per-protocol population.

The safety data will be summarized based on the ITT population. The primary and secondary endpoint analyses will also be performed on the ITT population.

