## **11.4 EFFECTIVENESS ENDPOINTS AND ANALYSIS METHODS**

Descriptive statistics on continuous variables will include mean, standard deviation, median, minimum, and maximum. Confidence intervals for change from baseline will be included for selected endpoints. Categorical variables will be summarized using frequency counts and percentages. Exact confidence intervals for point estimates may be provided. Statistical testing will be one-sided with a significance level of 0.025 or two-sided significance level of 0.05 unless specify otherwise. Data listings of individual subject data may be provided.

As described above, the primary analyses of the primary and secondary effectiveness endpoints will be based on the PP population, although the analyses will also be performed on the ITT population. The safety data will be summarized based on the ITT population.

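### The 80% power stated for 91 evaluable eyes comes from a normal approximation; the binomial test planned for the primary endpoint, read as exact and one-sided, has 77.3%

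*Combined protocol and SAP*

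**What the plan says.** Section 11.1 (Primary Effectiveness Endpoint) tests whether the proportion of eyes with at least a 20% fall in unmedicated mean diurnal IOP exceeds 0.40. The method it names is an adjusted normal approximation at one-sided 0.025, and the number it arrives at is 91. The claim attached to that number is: "eyes with evaluable data at 12 months provides a statistical power of 80% at a true" proportion, which the section sets at 0.55. The same section makes the success criterion a one-sided p-value below 0.025 and allows formal conclusions on the secondary endpoints only if it is met.

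Section 11.4.1 describes the analysis. For the interval: "The binomial distribution will be used to derive the exact 95% confidence interval of the percent". The test is put separately, and says that the observed "proportion will be compared against the performance goal of 0.4 (or 40%) based on binomial distribution". The word exact is attached to the interval only; the test itself is not named.

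Section 11.4 adds a general rule: "Statistical testing will be one-sided with a significance level of 0.025 or two-sided significance level of 0.05 unless specify otherwise". Section 11.2 makes the per-protocol set primary: "The primary analyses on the primary and secondary endpoint analyses will be carried out on the per-protocol population".

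**The concern.** The power statement and the planned analysis rest on different distributions. A normal approximation treats the number of successes as continuous. An exact binomial test can reject only at whole counts, and its true size usually falls below the nominal 0.025. When it falls well below, power is lost, and a power figure from the approximation can overstate what the test delivers at a particular sample size.

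Two things are at stake. The first is whether 91 evaluable eyes give the stated 80% chance of meeting the goal if the true rate is 55%. The second is whether the success rule is unique, because the test is not named and section 11.4 mentions both a one-sided and a two-sided level. The secondary endpoints are gated on this one result, so a borderline count should have only one possible reading.

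**Working it through.** **Inputs.** Performance goal p0 = 0.40, assumed true rate p1 = 0.55, one-sided alpha = 0.025, n = 91 evaluable eyes and stated power 80%, all from section 11.1. The form of the analysis is from section 11.4.1. Here p0(1 − p0) = 0.24 and p1(1 − p1) = 0.2475.

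**Step 1: reproduce the plan's figure.** The normal formula without correction is

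n0 = [(1.96 × √0.24 + 0.8416 × √0.2475) / 0.15]² = 84.50.

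With the continuity correction,

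n = (n0/4) × [1 + √(1 + 2/(n0 × 0.15))]² = 91.05.

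Power at n = 91 with the same correction is

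Φ{[0.15 × √91 − 1/(2√91) − 1.96 × √0.24] / √0.2475} = Φ{(1.4309 − 0.0524 − 0.9602) / 0.4975} = Φ(0.841) = 79.98%.

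The stated 80% at 91 is therefore the continuity-corrected normal result.

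**Step 2: the exact one-sided binomial test at n = 91.** The cutoff is the smallest count whose upper tail probability under 0.40 is below 0.025.

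| Successes | P(X ≥ r) at 0.40 | Exact 95% lower limit | P(X ≥ r) at 0.55 |
|---|---|---|---|
| 46 | 0.0266 | 39.9% | 83.1% |
| 47 | 0.0161 | 40.9% | 77.3% |

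A count of 46 fails and 47 passes. Power is 77.3%, so the shortfall is 80 − 77.3 = 2.7 points and the chance of missing the goal is 100 − 77.3 = 22.7%. The exact interval gives the same cutoff, because its lower limit first exceeds 40% at 47.

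**Step 3: would the test that matches the sizing formula do better?** The continuity-corrected z statistic at 46/91 is (0.5055 − 0.4 − 0.5/91) / √(0.24/91) = 1.947, below 1.96. That test also needs 47 successes, so its true power is also 77.3%. The next lower cutoff, 46, has 83.1% power, but its true size is 0.0266, above the plan's 0.025.

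**Step 4: how much depends on n being exactly 91.**

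| Evaluable eyes | Cutoff | Exact power at 0.55 |
|---|---|---|
| 88 | 45 | 79.9% |
| 89 | 46 | 76.9% |
| 90 | 46 | 80.2% |
| 91 | 47 | 77.3% |
| 92 | 47 | 80.5% |
| 93 | 48 | 77.7% |
| 94 | 48 | 80.8% |
| 95 | 48 | 83.6% |

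From 94 to 400, the range checked, exact power never drops below 80%; the lowest value is 80.8%, at 94. With n fixed at 91 and a cutoff of 47, power reaches 80% at a true rate of about 55.5%.

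**Step 5: the boundary count under other readings of the test.** At 46/91 the one-sided exact p-value is 0.0266 (fail) and the doubled two-sided value is 0.053 (fail). The two-sided exact p-value that sums point probabilities is 0.042 (pass at 0.05), and the one-sided mid-p value is 0.0214 (pass at 0.025).

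**The case against.** The strongest reply is that nothing in section 11.1 is wrong on its own terms. It names an approximation, and the figure follows from it. The continuity correction exists to mimic the exact tail, and it has already raised the requirement from 84.5 to 91. What remains is saw-tooth error: the mean exact power over n = 88 to 94 is 79.0%, and 91 happens to be a low point. The rest of section 11.1 and the number of subjects are redacted. If attrition or secondary-endpoint sizing leads to 94 or more evaluable eyes, the shortfall disappears. The one-sided or two-sided question is also largely settled, since section 11.1 sets a directional alternative and a one-sided criterion, and the general rule in section 11.4 yields to a specific one.

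Much of this stands. It is a mismatch between sizing method and analysis, it is small, and it depends on the exact count. The sidedness point is secondary: a two-sided p-value is not the criterion in section 11.1. That criterion does not by itself exclude a mid-p version, so naming the test still has some value.

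The reply does not rescue the stated figure. The 80% is claimed for 91 evaluable eyes, so redacted enrolment and attrition do not bear on it. At that number neither the exact test nor the continuity-corrected z test delivers 80%, and the only way to reach it at 91 is a rule whose true size exceeds 0.025.

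**Conclusion.** The concern holds, and its size is modest. For 91 evaluable eyes and a true rate of 0.55, the planned analysis has 77.3% power, not 80%. The error is on the conservative side for type I error (0.0161 against 0.025), so it would not undermine a positive finding; it slightly understates the risk of a negative one.

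This rests on two assumptions. First, the binomial comparison is the exact one-sided test. The plan does not say so in those words, but the one-sided criterion in section 11.1 and the exact interval in section 11.4.1 both lead to the 47-success cutoff. Second, the adjusted normal approach means the continuity-corrected formula, which reproduces the stated figure. The power the trial will actually have depends on how many eyes are evaluable in the per-protocol set, which the visible text does not show.

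**What to change.** In section 11.1, restate the power for 91 evaluable eyes as about 77% at a true rate of 0.55 under the exact one-sided binomial test, with 47 successes needed if exactly 91 eyes are evaluable. Add that exact power is at or above 80% for every evaluable number from 94 (lowest 80.8%; checked to 400).

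In section 11.4.1, name the primary test as the exact one-sided binomial test at 0.025, consistent with the exact 95% interval.

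Do not adopt 90 or 92 as a target because its exact power happens to exceed 80%: one eye more or fewer gives 76.9%, 77.3% or 77.7%.

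The cost is one or two sentences in section 11.1 and a few words in section 11.4.1. No extra patients are needed and the analysis does not change; the stated power becomes 2.7 points less favourable.

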## **11.2 ANALYSIS POPULATIONS**

The intent-to-treat (ITT) analysis population includes all subjects who are enrolled and treated, regardless of whether or not they have a protocol deviation. The per-protocol analysis population (PP) is a subset of ITT, which includes all subjects who have ab-interno transluminal viscoelastic delivery and trabeculotomy, 12 month IOP (or hypotensive medications washed out IOP if the medications can be washed out) and medication data, and have no clinically significant protocol deviations. It should be noted that the ITT subjects with an uneventful study procedure but with SSIs before the 12-month visit will be included in the PP population even if they do not have the 12-month IOP and medication data. The primary analyses on the primary and secondary endpoint analyses will be carried out on the per-protocol population.

The safety data will be summarized based on the ITT population. The primary and secondary endpoint analyses will also be performed on the ITT population.

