## 2 STUDY OBJECTIVE

To prospectively assess the clinical effect of ab-interno transluminal viscoelastic delivery and trabeculotomy performed with the OMNI Surgical System in pseudophakic eyes on intraocular pressure (IOP) and the use of IOP-lowering medications in patients with open angle glaucoma (OAG).

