## **15 DEVICE FAILURES AND MALFUNCTIONS**

All device failures or malfunctions should be recorded on the Customer Experience Form and reported to Sight Sciences Customer Service [contact]).

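### The deciding per-protocol set is restricted to eyes that had both viscoelastic delivery and trabeculotomy, so eyes with a component not delivered drop out of the test against the 40% goal

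*Combined protocol and SAP*

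**What the plan says.** Section 11.2 sets up two populations. ITT "includes all subjects who are enrolled and treated, regardless of whether or not they have a protocol deviation". PP is a subset of ITT "which includes all subjects who have ab-interno transluminal viscoelastic delivery and trabeculotomy, 12 month IOP" (washed-out IOP where washout is possible) and medication data, with no clinically significant deviation. Having the procedure is thus a condition of its own, separate from having 12-month data.

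One clause brings failures back: "ITT subjects with an uneventful study procedure but with SSIs before the 12-month visit will be included in the PP population", even without 12-month data. It is limited to SSIs, and to procedures that were uneventful.

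On which set decides, Section 11.2 says: "The primary analyses on the primary and secondary endpoint analyses will be carried out on the per-protocol population". Section 11.4 repeats it: "the primary analyses of the primary and secondary effectiveness endpoints will be based on the PP population, although the analyses will also be performed" on ITT. Section 11.1 ties the effectiveness conclusion, and the gate to the secondary endpoints, to the primary endpoint test.

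Four other places bear on the point:

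- Section 2 gives the objective: "To prospectively assess the clinical effect of ab-interno transluminal viscoelastic delivery and trabeculotomy performed with the OMNI Surgical System".
- Section 9.9 treats every subject with a secondary IOP-lowering intervention as a treatment failure in the endpoint analyses, with no condition on how the surgery went.
- Section 9.7 has the region and extent of trabeculotomy recorded on the case report form.
- Section 15 says: "All device failures or malfunctions should be recorded on the Customer Experience Form".

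**The concern.** In a single-arm device study, whether both components can be delivered is a result of the device and the technique. It becomes known only once surgery has begun. A deciding set that requires both components therefore estimates the responder rate given procedural success, not the rate among eyes in which a surgeon sets out to use the device. There is no control arm in which a similar exclusion could offset the effect. If incomplete eyes do worse than completed ones, the PP proportion is too high for the attempted population and can clear the 40% goal when the attempted population would not.

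The limit on the SSI clause adds an inconsistency. Take an eye with an eventful procedure and then an SSI before month 12. Under Section 9.9 it is a failure and the subject is later withdrawn, so 12-month data will often be missing. Under Section 11.2 the clause that restores SSI eyes does not reach it. A failure by one section can be absent from the deciding analysis by the other.

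**Working it through.** **Inputs.** Null rate 0.40, design rate 0.55, one-sided level 0.025 and 91 evaluable eyes (Section 11.1); test based on the binomial distribution (Section 11.4.1). The documents give neither a rate of incomplete procedures nor a response rate in such eyes. Both are assumed below.

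**The plan's sample size.** Normal approximation: n = [1.960·√(0.4·0.6) + 0.842·√(0.55·0.45)]² / 0.15² = 84.5. With continuity correction: (n/4)·[1 + √(1 + 2/(n·0.15))]² = 91.05. This reproduces the stated 91.

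**The pass rule.** For X ~ Binomial(91, 0.40), P(X ≥ 46) = 0.0266 and P(X ≥ 47) = 0.0161. The test needs 47 responders (51.6%), and its true size is 1.6%.

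**Chance of passing when the attempted population is exactly at the goal.** Let q be the share of attempted eyes with incomplete delivery and r their response rate. If the rate in all attempted eyes is 0.40, the PP rate is (0.40 − q·r)/(1 − q). For q = 0.05 and r = 0.20 this is 0.39/0.95 = 0.411. The chance of passing is P(X ≥ 47) with n = 91 at that rate:

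| Response in incomplete eyes (assumed) | q = 3% | q = 5% | q = 10% |
|---|---|---|---|
| 0% (worst case): PP rate | 41.2% | 42.1% | 44.4% |
| 0%: chance of passing | 2.9% | 4.2% | 10.1% |
| 20%: PP rate | 40.6% | 41.1% | 42.2% |
| 20%: chance of passing | 2.2% | 2.6% | 4.4% |
| 40%: chance of passing | 1.6% | 1.6% | 1.6% |

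The nominal level is 2.5%.

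**Sensitivity of a given result.** Add excluded eyes as non-responders and recompute the exact one-sided p against 0.40:

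- At the threshold: 47/91, p = 0.0161 (passes); 47/92, p = 0.0203 (passes); 47/93, p = 0.0254 (fails); 47/96, p = 0.0467 (fails).
- Near the design rate (0.55 × 91 ≈ 50): 50/91 plus five is 50/96, p = 0.011 (still passes).

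**Power if incomplete eyes enter as non-responders.** Suppose 91 completed eyes respond at 0.55 and k incomplete eyes are added. Power is P(X ≥ c) for X ~ Binomial(91, 0.55), with c the critical value at 91 + k. This gives 77.3% (k = 0, c = 47), 70.5% (k = 2, c = 48) and 62.9% (k = 5, c = 49).

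**The case against.** Several counter-arguments carry weight.

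- **ITT is also analysed.** A reader might infer that delivery failures can never count against the device. The documents do not support that. Section 11.2 commits to it: "The primary and secondary endpoint analyses will also be performed on the ITT population". Because PP is a subset of ITT with the procedure as an added condition, ITT plausibly contains eyes that did not have both components, and a gap between the two results would be visible. What remains is that ITT has no stated role in the decision, and *treated* is not defined for an attempted but incomplete case.
- **No completion threshold.** *Have* is not *completed*, and Section 9.7 expects the extent of trabeculotomy to vary. An eye with a partial trabeculotomy and some viscoelastic can be read as inside PP. The exclusion is clear only where a component was not delivered at all. For partial delivery the plan is open, which is itself a reason to define it before data are seen.
- **The data are not lost.** Section 15 does not say that the Customer Experience Form replaces trial records. Extent goes on the case report form, intraoperative adverse events are summarised on ITT (Section 11.5.1), and deviations are documented (Section 14). The readable text still asks for no count of incomplete deliveries.
- **Redaction.** Parts of 9.7 and 11.4.1 are blacked out and may hold a scoring rule for failed procedures. Such a rule would have to override the readable PP definition to bring back an eye that lacks a component.
- **Inflation may be small.** A reader might take 10.1% as the error rate of the plan. It needs both the top of an assumed range and no response at all in incomplete eyes. An eye that received one component can respond, and if such eyes respond at 40% nothing is inflated.

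**Conclusion.** The concern holds for the deciding analysis. As the readable text stands, the test against the 40% goal is conditional on both components having been delivered, and an SSI after an eventful procedure can be missing from it despite Section 9.9. The direction favours the device whenever incomplete eyes respond less often than completed ones.

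The size cannot be fixed from the documents. Over the assumed range it runs from no inflation to a chance of passing of 10.1%. With a 20% response in incomplete eyes, the nominal 2.5% is exceeded at 5% and 10% incomplete delivery, but not at 3%. Two excluded non-responders reverse a result exactly at the threshold, while a result near the design rate withstands five. This should be corrected in the plan. It does not show that the study's conclusion would be wrong.

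**What to change.** 1. Run the primary test on all eyes in which the OMNI procedure was attempted, meaning the device was introduced into the eye. Either define *treated* in ITT that way and make ITT primary, or drop the both-components condition from the deciding set.
2. Score eyes with incomplete delivery by their observed 12-month unmedicated diurnal IOP.
3. Score any eye with a secondary IOP-lowering intervention as a non-responder, as Section 9.9 already states, and remove the *uneventful* condition from Section 11.2 so that the two sections agree.
4. Report the number of attempted eyes with incomplete viscoelastic delivery or trabeculotomy.
5. Keep the completed-procedure PP result as a supportive analysis.

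The cost is a change of wording in the statistical sections, using data that the scheduled visits and case report forms already collect. The headline proportion may be slightly lower. Power falls to the extent that incomplete eyes do not respond, with the worst-case figures given in the working.
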